4.2.2. Acute treatment phase

When the patient bears more than 4 minutes of neurostimulation, he/she is included in the trial, and the neurostimulation continues for the 56 remaining minutes of the stimulation. The patient will be randomized to receive either:

- Verum stimulation, with square pulse current (100 Hz, 250 μ s) at a linearly increasing intensity starting at 0 mA up to a maximum of 16 mA after 14 minutes, then remaining stable for the rest of the session (46 minutes), OR
- Sham stimulation with felt paresthesia.

At the end of the one-hour treatment period the patient gives again an estimate of the pain on the same VAS.

During the treatment, the patient can stabilize the intensity by pressing the button or can stop the treatment. The device can also be stopped accidentally, what interrupts the treatment. When stopped, voluntarily or accidentally, the device may not be restarted.

Duration, intensity and/or interruption will be recorded for each patient thanks to a built-in electronic system in the device.

In any case, the patient gives the estimate of the pain after 60 minutes.

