4.2.4. Drop-outs, intention-to-treat and last value carried forward

a) During the treatment one-hour phase

If the patient takes rescue medication before 1 hour, it is a drop-out because the action of the medication affects the pain estimate at 1 hour.

If the patient stops the one-hour treatment and leaves the clinic, it is a drop-out because there is no pain estimate at 1 hour.

If the device stopped working accidentally, it is a drop-out because of technical reason.

On the other hand, if a patient does not get the full Cefaly acute treatment (does not want to complete the 1 hour stimulation), but stays available for the 2 hours of the protocol, this patient is kept in the trial and considered as an intention-to-treat patient (as opposed to per protocol patient).

b) During the post treatment phase

If the patient takes rescue medication before 2 hours, only the one-hour pain intensity estimate has been measured; the last value carried-forward method will be applied for 2 and 24 hours pain intensity estimate.

If the patient takes rescue medication at 2 hours or after 2 hours, the last value carried-forward will be applied for the 24 hours pain intensity estimate.

[figure not shown]

Figure 1 - Study flowchart

5. Subjects

The study will include 90 men or women.

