8.2.2. Statistical methods

- All relevant general, safety and efficacy data will be descriptively summarized at each time point.
- Continuous data will be summarized by the number of subjects (N), the arithmetic mean, the standard deviation, the coefficient of variation as a percentage (CV%), the median, the inter-quartile range, the minimum and the maximum value.
- Categorical data will be summarized by absolute (N) and relative (%) frequency tables.
- Where considered as relevant, the study data will also be graphically depicted.

- Imputation of missing data will be performed according to the last value carried forward method.
- Analyses will be conducted on an intent-to-treat (ITT) basis, i.e. including all subjects who used the study device for more than 4 minutes (see in exclusion criteria 8. Allodynia), did not take rescue medication before the 1 hour and reported pain at 1 hour.
- A sub-analysis of the per-protocol patients (those receiving the complete 1-hour treatment) will be performed as well.

9. Management of adverse events

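### An accidental device stop makes a patient a drop-out under 4.2.4 but an intention-to-treat patient under 8.2.2, so membership of the primary analysis set is contradictory

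*Combined protocol and SAP*

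**What the plan says.** Three sections of the combined protocol and SAP bear on this.

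- **4.2.2 (acute treatment phase)** foresees the event: "The device can also be stopped accidentally, what interrupts the treatment". It applies one rule to both kinds of stop, "When stopped, voluntarily or accidentally, the device may not be restarted", and ends: "In any case, the patient gives the estimate of the pain after 60 minutes". It also says that a built-in system logs how long and how strongly each patient was stimulated and any break. It does not say that the log captures the reason for a stop.
- **4.2.4 (drop-outs)** lists three kinds of drop-out in the treatment hour: rescue medication before 1 hour, leaving without a 1-hour score, and the technical one, "If the device stopped working accidentally, it is a drop-out because of technical reason". By contrast, a patient who chooses not to complete the hour but remains available for the full 2 hours is retained: "this patient is kept in the trial and considered as an intention-to-treat patient (as opposed to per protocol patient)".
- **8.2.2 (statistical methods)** defines the intention-to-treat set as "including all subjects who used the study device for more than 4 minutes", with the further conditions that they "did not take rescue medication before the 1 hour and reported pain at 1 hour". The per-protocol sub-analysis is limited to patients who received the complete hour.

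The primary outcome (section 3) is the change in pain score at 1 hour. No section says whether 4.2.4 or 8.2.2 prevails.

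**The concern.** The other two drop-out rules in 4.2.4 each give a reason tied to the 1-hour score: it is affected by medication, or it is absent. Both agree with 8.2.2. The accidental-stop rule gives no such reason, because the score can exist and be unmedicated. It is the only one of the three that 8.2.2 does not share.

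Two things are at stake. First, an analyst could build the primary set in two ways and cite the protocol for either; if this is left open, the choice could be made after the data are seen. Second, under 4.2.4 two patients with the same shortened stimulation and the same 1-hour score are treated differently according to how the stop is described. That is an exclusion after randomisation from a set called intention-to-treat, and the documents give no rule for classifying a stop.

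**Working it through.** **Step 1: set the rules side by side.**

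| Patient | 4.2.4 | 8.2.2 main set | 8.2.2 per-protocol |
|---|---|---|---|
| Accidental stop at minute 30, stays, no rescue, gives 60-minute score | Drop-out | In | Out |
| Voluntary stop at minute 30, stays the 2 hours, no rescue, gives 60-minute score | Kept | In | Out |
| Rescue before 1 hour | Drop-out | Out | – |
| Leaves, no 1-hour score | Drop-out | Out | – |
| Accidental stop within the first 4 minutes | Drop-out | Out | Out |

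Only the first row conflicts. The conflict is confined to accidental stops after more than 4 minutes, with no rescue before 1 hour and a reported 1-hour score.

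**Step 2: reproduce the plan's sample sizes (8.2.1).** Inputs: SD 2.42, differences 2.83 (1 hour) and 2.40 (2 hours), two-sided 5%, 80% power, two-sample t-test.

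- Difference 2.40: 16.98, so 17 per group, as stated.
- Difference 2.83, the primary time point: 12.52, so 13 per group.
- Rescue use at 24 hours, 71% against 41.33%, pooled proportion test without continuity correction: 43 per group, as stated.

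**Step 3: effect on power and precision.** The documents give no accidental-stop rate, so the losses below are assumptions.

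- Primary outcome: the plan requires 17 and recruits 45 per group, a margin of 45 − 17 = 28. At 36 per group (nine lost from each), power for a difference of 2.83 is still 99.8%.
- If 5% of sessions stopped accidentally, 0.05 × 90 = 4.5 outcomes would be lost, and the standard error would rise by the factor 1/√0.95 = 1.026.
- Rescue use, a secondary outcome: power is 82.1% at 45 per group, 80.3% at 43 and 79.3% at 42.

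**Step 4: possible shift in the primary estimate.** The plan gives no baseline mean. Its percentages imply 2.83 / (0.59 − 0.10) = 2.83 / 0.49 = 5.78. The planned fall is then 0.59 × 5.78 = 3.41 in verum and 0.10 × 5.78 = 0.58 in sham. If a fraction p of an arm stops and those patients fall by d less than the rest, excluding them raises that arm's mean fall by p × d. Assume that stopped patients achieve half the planned fall, so d = 1.70 in verum and 0.29 in sham.

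| Assumed accidental stops | Verum shift | Sham shift | Change in difference |
|---|---|---|---|
| 10% verum, 0% sham | 0.10 × 1.70 = 0.17 (3.24 to 3.41) | 0 | +0.17 |
| 5% in each arm | 0.05 × 1.70 = 0.085 | 0.05 × 0.29 = 0.015 | +0.07 |
| 0% verum, 10% sham | 0 | 0.10 × 0.29 = 0.03 | −0.03 |

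For scale, 0.17 / 2.83 = 6% of the planned difference. The standard error of the difference at 45 per group is 2.42 × √(2/45) = 0.51, so 0.17 is about one third of it.

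**The case against.** **Collecting a score is not the same as analysing it.** Section 4.2.2 governs data collection, so taking the 60-minute score does not by itself contradict 4.2.4. This stands: the direct conflict is between 4.2.4 and 8.2.2. Section 4.2.2 shows only that the discarded score would exist.

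**The wording differs.** Section 4.2.2 speaks of the device being stopped, 4.2.4 of its ceasing to work, which could mean malfunction only. On that reading the conflict with 8.2.2 remains, and an accidental button press has no category in 4.2.4. The term drop-out is not formally defined either, but the contrast with the voluntary stopper who is kept supports reading it as removal from the analysis.

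**Excluding technical failures is a legitimate question.** The per-protocol set also removes voluntary stoppers, so a set without technical failures alone is a different analysis. This stands, and it can be a sensitivity analysis. It does not justify two definitions of the main set.

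**Stronger readings that the documents do not support.**

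- A reader might infer that the exclusion favours verum. Nothing gives stop rates by arm, and the direction can reverse. Patients who hold the intensity complete the session, and voluntary stoppers who stay are kept, so neither behaviour leads to removal under this rule. Section 6.5 describes the sham sensation as similar.
- A reader might infer that stops are labelled afterwards by someone who knows the allocation. The documents do not say who classifies a stop or when. Section 7.3 blinds the investigator and the research coordinator, and a reason recorded at the time by blinded staff is equally consistent with the text.
- A reader might infer that the trial has only 45 − 43 = 2 patients per group to spare. The 43 belongs to 24-hour rescue use, not to the primary outcome.

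**Conclusion.** The contradiction holds. For the patient in the first row of the comparison, 4.2.4 and 8.2.2 give opposite answers about the primary analysis set, and neither is given precedence. Following 4.2.4 removes a valid, measured primary outcome after randomisation on a distinction for which the plan gives no classification rule and which the device log is not said to record.

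The likely size is modest. Under the plan's own effect and SD, loss of primary power is negligible. The shift in the primary difference ranged from −0.03 to +0.17 points across the scenarios shown. These rest on assumed stop rates, an assumed half effect in stopped patients and a baseline inferred from the sample-size figures. If stopped patients did better than the rest of their arm, the signs would change. The point is worth correcting because it concerns who is in the primary analysis, not because a large bias has been shown.

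**What to change.** Delete the accidental-stop sentence from the drop-out list in 4.2.4. In its place, state that a patient whose session is interrupted after more than 4 minutes, voluntarily or accidentally, who took no rescue before 1 hour and who reported 1-hour pain, stays in the main intention-to-treat analysis as 8.2.2 defines it and is left out only of the per-protocol set. Keep all three conditions in the sentence, so that it does not readmit patients whom 8.2.2 excludes. Report the number and timing of interruptions by arm from the device log. Make the change before the allocation is revealed to those analysing the data.

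The cost is one sentence deleted, one added and a short table. The estimate may be slightly diluted by interrupted sessions. If the sponsor wants the effect without technical failures, a sensitivity analysis excluding those alone can be added, with the reason for each stop recorded at the time by blinded site staff. The change concerns analysis membership only and leaves the conduct of the session untouched.

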Recently, after having demonstrated a sedative effect (1), a multi-center, randomized, double-blind, sham-controlled trial has shown the efficacy and safety of external trigeminal nerve stimulation (e-TNS) with the Cefaly® device for the preventive treatment of episodic migraine (2). Safety and patient satisfaction has been further confirmed by a prospective study on 2,313 patients (3).

Many patients in Europe have reported benefit using the device only during attacks. In past few years, small studies have been performed using the Cefaly® device as an acute treatment:

- A medical lab in France ("Spincontrol") implemented an open clinical trial during 28 days on 32 patients suffering from frequent tension-type headache but not migraine. 66% reported pain relief using the device during an attack.
- University of Liege conducted a pilot trial on migraine patients (4). Ten patients were asked to apply the Cefaly® device as an acute treatment for 3 attacks. Electro-stimulation provided complete pain relief in 13% of attacks, delayed the need for acute medication use by more than 30 minutes in 20%, had no effect in 57% and increased the pain in 10%. However, there were flaws in the protocol design, including the short duration of the session (20 minutes), which is not sufficient to provide relief based on experiential feedback from migraineurs. In addition, the number of attacks treated was too small, as patients may require several sessions to adapt to and allow the intensity of stimulation to rise to a therapeutic level (otherwise it is under a minimum threshold of efficacy).
- Kozminsky (5) assessed whether the Cefaly® device was effective and well-tolerated as rescue therapy for migraine symptoms lasting 72 hours or longer. t-SNS (or e-TNS) therapy with the Cefaly device brought about a reduction of migraine-related pain (average minus 46%) as rescue therapy in these patients. e-TNS therapy via the Cefaly® device was well-tolerated, and most patients reported that they would consider home therapy if it were affordable.

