4.2. Experimental protocol

Patients having a stabilized migraine attack will be recruited during a standard care visit or at an on-demand appointment. They will report their pain score before the treatment (recruitment phase), after 1 hour of treatment (acute treatment phase) and finally 2 hours after the beginning of the treatment (post-treatment phase). At that moment (2 hours after the beginning of the treatment), patients will receive rescue medication if necessary. Rescue medication intake will be reported during the 24 hours following the beginning of the treatment. Pain score at 24 hours after the treatment will be reported as well. The overall study flow is illustrated in Figure 1. During the different phases the investigator will monitor adverse events.

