4.2.3. Post-treatment phase

Two hours after the beginning of the treatment the patient will have to give a new estimate of the pain on the VAS, provided that the patient didn't take a rescue medication before.

After the 2 hours, if needed usual rescue treatment can be administrated to the patient. If so, this is recorded by the investigator.

Patients will also be instructed to record the pain level 24 hours after the beginning of the treatment. They will be contacted to report this pain level and whether or not rescue medication was taken within the 24 hours following the beginning of the treatment. In case of rescue medication intake within the 24 hours following the treatment the pain level at 24 hours will not be taken into account.

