7.1. Measures

Pain score. In order to evaluate the modification of pain score from baseline to 1-hour treatment and to 2-hour treatment, patients will be asked to give an indication on the pain level using a visual analogue scale (VAS) counting eleven levels (0 = no pain, 10 = maximum pain) at the recruitment phase (before applying the treatment), right after the treatment phase (1 hour), 2 hours after the beginning of the treatment and at 24 hours after the beginning of the treatment.

Rescue medication after the treatment. The investigator will also record whether the patient uses another acute medication right after the 2 hours. Patients will also be contacted 24 hours after the beginning of the treatment to report whether or not rescue medication was taken within the 24 hours following the beginning of the treatment.

The following table depicts when the different measures will be made:

	Baseline	1 hour	2 hours	24 hours
Pain score	●	●	●	●
Rescue medication intake			●	●

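### For rescue taken after the 2 h visit (or, less expectedly, between 1 h and 2 h) no pain score is recorded at rescue, so section 4.2.4 carries forward a score that may predate a relapse

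*Combined protocol and SAP*

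**What the plan says.** After the baseline score, section 7.1 schedules pain scores "right after the treatment phase (1 hour), 2 hours after the beginning of the treatment and at 24 hours after the beginning of the treatment". Its table has no row triggered by rescue. Section 4.2.3 takes the 2 h score "provided that the patient didn't take a rescue medication before".

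Section 4.2.4 sets the values used after rescue:

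- Rescue between 1 h and 2 h: "If the patient takes rescue medication before 2 hours, only the one-hour pain intensity estimate has been measured", and "the last value carried-forward method will be applied for 2 and 24 hours pain intensity estimate".
- Later rescue: "If the patient takes rescue medication at 2 hours or after 2 hours, the last value carried-forward will be applied for the 24 hours" score.

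Four other places bear on this:

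- Section 4.2 places the 2 h score and the first permitted rescue at the same visit: "At that moment (2 hours after the beginning of the treatment), patients will receive rescue medication if necessary".
- Section 6.6 bars medication during the first 2 h, yet provides carry-forward for a patient who wants rescue between 1 h and 2 h.
- Section 3 limits the 2 h and 24 h pain outcomes to patients without rescue, and section 4.2.3 disregards the 24 h score after rescue.
- Section 8.2.2 applies carry-forward to missing data in general and names no sensitivity analysis.

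**The concern.** Rescue is usually taken because pain persists or has come back. Where it has come back after the last scheduled score, the pain that prompted rescue is never measured, and the value analysed at 24 h is one from before the relapse. Someone at 3 points at 2 h, back at 6 points at 8 h and then medicated enters the 24 h mean as a 3.

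The carried score can be up to 1 h old at rescue between 1 h and 2 h, and nearly 22 h old at rescue just before 24 h. The loss cannot be made good later. The 24 h contact described in sections 4.2.3 and 7.1 asks for the pain level and whether rescue was taken, but not when, nor how bad the pain was beforehand. (The CRF is listed as an annex and is not reproduced.) At stake is the meaning of the 24 h mean change and, to a much smaller extent, the 2 h mean change.

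**Working it through.** **1. The plan's own figures (section 8.2.1).** Both sample sizes reproduce, and this point does not alter them.

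- Pain score: a two-sample t-test with difference 2.40, SD 2.42, two-sided alpha 5% and power 80% gives 16.98, so 17 per group.
- Rescue use: the pooled two-proportion formula for 71% v 41.33% is n = [1.960 × √(2 × 0.5617 × 0.4383) + 0.842 × √(0.71 × 0.29 + 0.4133 × 0.5867)]² / 0.2967² = 42.7, so 43 per group.

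**2. How many 24 h scores would be carried.** With 45 per group, 0.4133 × 45 = 18.6 verum and 0.71 × 45 = 32.0 sham patients would be rescued within 24 h. That is 50.6 of 90, or 56%. These rates come from a previous study of another treatment. The documents do not say how the rescues divide between before, at and after the 2 h visit, so 56% is the share carried, not the share carried with an out-of-date score.

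**3. Relief implied by the planning figures.** Baseline is 2.40 / (0.55 - 0.14) = 5.85 points; the 1 h figures give 2.83 / (0.59 - 0.10) = 5.78. Mean 2 h relief is 0.55 × 5.85 = 3.22 (verum) and 0.14 × 5.85 = 0.82 (sham).

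**4. Bias formula.** Let r be the rescue rate in an arm and x the mean relief in the carried score among its rescued patients. Let f be the share of rescued patients who took rescue after the 2 h visit and were back at baseline pain by then, taken as equal in both arms. Measured against pain at rescue, carry-forward overstates mean 24 h relief in an arm by r × f × x. The difference between arms is shifted by f × (0.4133 × x_verum - 0.71 × x_sham).

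**5. Results.** The documents give neither f nor x, so these are assumptions.

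| Assumption | Verum | Sham | Shift in difference |
|---|---|---|---|
| Arm's mean 2 h relief, f = 100% | 0.4133 × 3.22 = 1.33 | 0.71 × 0.82 = 0.58 | +0.75 |
| Same relief, f = 50% | 0.67 | 0.29 | +0.37 |
| Same relief, f = 25% | 0.33 | 0.15 | +0.19 |
| Pain at rescue equals last score | 0 | 0 | 0 |
| 1 point of relief in both arms, f = 100% | 0.41 | 0.71 | -0.30 |

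The first row would turn a true difference of 2.40 - 0.75 = 1.65 into 2.40, if patients without rescue keep their 2 h relief.

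**6. What decides the sign.** The shift favours verum only if x_verum / x_sham exceeds 0.71 / 0.4133 = 1.72. The arms' overall mean reliefs have a ratio of 0.55 / 0.14 = 3.93, but rescued patients need not resemble their arm's average.

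**7. The 2 h endpoint.** Only rescue between 1 h and 2 h can affect it. No expected number is given, so no size is computed.

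**The case against.** Several points on the other side stand and set the limits of this one.

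- **Rescue at 2 h.** A reader might infer that no rescue dose is preceded by a score. That is not so: at the 2 h visit the score and the rescue coincide, and the carried value is current. The 2 h endpoint is little exposed, since section 6.6 bars earlier medication.
- **Direction.** A reader might infer a spurious advantage for verum. The +0.75 needs every rescue after 2 h, average relief among rescued patients, and full relapse in all of them. Patients who never responded carry little relief, and more sham than verum patients are expected to be rescued, which can reverse the sign.
- **Relapse is recorded elsewhere.** A reader might infer that the trial cannot tell lasting relief from relapse. The two rescue-use outcomes count a relapse that led to medication as a failure, and the trial is sized on the 24 h comparison. They do not, however, correct the mean pain change or separate relapse from pain that was never relieved.
- **The pilot.** The introduction says stimulation "delayed the need for acute medication use by more than 30 minutes in 20" per cent of attacks. That is a delay in medication; it does not report pain returning after relief. The study had ten patients and 20-minute sessions, which the protocol itself calls a flaw.
- **Section 3 may exclude rescued patients altogether.** If so, no carried score enters these endpoints. But sections 4.2.4 and 8.2.2 say otherwise, so the governing rule is unsettled. Exclusion would instead select patients on an event after randomisation.

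It can also be argued that reconciling the rules and adding a sensitivity analysis would suffice without new data. That would show how far the result depends on the rule, but not what the pain was at rescue.

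**Conclusion.** The point holds for rescue after the 2 h visit and, with less weight, for rescue between 1 h and 2 h. In those cases section 4.2.4 uses a score that may predate a relapse, and nothing collected can show whether it did. It does not hold for rescue at the 2 h visit, nor for a patient whose carried score shows no relief.

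The shift in the 24 h difference is about +0.75, 0 or about -0.30 points in the three main cases worked. These are illustrations, not bounds: they rest on borrowed rescue rates and on assumed relapse and carried relief, and the sign is not determined. The size matters only if carry-forward, rather than section 3's restriction, governs the analysis. The 1 h primary outcome, the rescue-use outcomes and the sample size are untouched. This is a cheap improvement, for secondary endpoints only.

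**What to change.** 1. Add one event-driven row to the section 7.1 schedule and the CRF: a VAS score with clock time immediately before the first rescue dose. It is recorded in clinic if the patient is still there, otherwise self-recorded at home and reported at the 24 h contact already planned. In section 4.2.4, carry this score forward, and use the last scheduled score only if it is missing.
2. Reconcile sections 3 and 4.2.3 with sections 4.2.4 and 8.2.2, so that a single stated handling of rescued patients applies to the 2 h and 24 h pain outcomes.
3. Add to section 8.2.2 a sensitivity analysis that treats rescue as no relief, with the baseline score carried forward.

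The cost is one question per rescued patient, one CRF line, a few sentences of text and one extra analysis. Some home scores will be missing or recalled, and those patients fall back on the present rule. When rescue may be given does not change.
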